4.2 SECONDARY

- Characterize the incidence of SSI as superficial incisional, deep incisional, and organ/space as defined by The American College of Surgeons National Surgical Quality Improvement Program (NSQIP) guidelines.
- Assess (or compare) the length of hospital stay between subjects who receive standard of care and incisional NPWT via PIMS or ActiV.A.C.

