5.0 STUDY DESIGN

5.1 STUDY DESCRIPTION

This study is a multi-center, open-label, randomized clinical trial conducted at Duke Cancer Institute and Indiana University to evaluate whether incisional NPWT can help reduce the rate of SSI in patients undergoing either colorectal or hepatopancreatobiliary surgery. Up to 170 subjects will be randomized in a 1:1 ratio to either conventional wound care (control group) or the incisional NPWT (experimental group) to ensure 138 evaluable subjects.

The primary study endpoint will be SSI within the laparotomy wound, as assessed on postoperative day 4-5 and the first postoperative clinic visit, which is anticipated to be within 30 days of surgery. Evaluable subjects are defined as those who have been randomized and completed both postoperative assessments. Non-evaluable subjects are those subjects who were randomized but did not complete both post-op visits. Non-evaluable scenarios include aborted surgeries, cancelled surgeries, death unrelated to study, and early device removal related to device malfunction. Screen failures are defined as those subjects not randomized.

Safety endpoints will be adverse events related to the device or dressing, including the presence of any abnormal skin findings (such as blisters or rash). These endpoints will be assessed from the day of surgery through the 30-day follow-up visit.

Subjects randomized to conventional wound care (control group) will have their skin incisions closed with skin staples, sutures, or surgical glue (per judgment of the treating physician), covered with sterile medical gauze and a form of adherent (tape or clear adhesive) for which the subject does not have any allergy. This dressing will be removed per the treating physician's discretion or institutional standards.

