5.2 RANDOMIZATION

Subjects who meet all inclusion criteria and no exclusion criteria and who consent to participate in the study will be randomized in a 1:1 ratio to receive either incisional NPWT via PIMS or ActiV.A.C or the standard-of care dressing following surgery. Randomization may occur up to 5 business days prior to surgery. If a subject is randomized and surgery is subsequently delayed, they will not be re-randomized even if outside the 5-day window.

Randomization will be stratified according to surgical site (colorectal vs hepatopancreatobiliary) and body mass index (BMI), < 30 vs ≥ 30.

Randomization using permuted block scheme will be done via REDCap Randomization Application. Please refer to the randomization manual for detailed instructions.

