10.1 STATISTICAL ANALYSIS

The primary analysis will include all randomized and evaluable patients but exclude ineligible patients or patients who are canceled from the study before receiving any wound care. SSI is defined as an infection that occurs within 30 days of operation. The primary endpoint is the SSI rate. The primary analysis of comparing the conventional wound care (control group) and the incisional V.A.C® (experimental group) will be conducted using a chi-square test for two-sample binomial probabilities with a one-sided significance level of 0.1. The observed SSI rates and 90% Upper Confidence Bound (UCB) estimates will be reported. Preoperative, intraoperative, and postoperative variables will be tabulated and appropriate summary statistics will be reported. As a secondary analysis, comparison of treatment groups for SSI will be adjusted for any significant preoperative, intraoperative, or postoperative variables using logistic regression.

For secondary endpoints, the incidence of SSI as superficial incisional, deep incisional, and organ/space will be estimated along with the 90% UCBs. The secondary endpoint length of stay is a continuous variable. A Wilcoxon rank sum test will be used to assess the significance of the difference between groups in median length of stay. Median length of stay, its range and quartiles will be reported.

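### Length of stay is compared by an unstratified Wilcoxon test although randomisation is stratified by surgical site and BMI; if either factor predicts stay, the test is conservative and loses some power (minor, optional)

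*Combined protocol and SAP*

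**What the plan says.** Section 4.2 makes length of stay a secondary objective: "Assess (or compare) the length of hospital stay between subjects who receive standard of care and incisional NPWT". Section 10.1 gives the method: "A Wilcoxon rank sum test will be used to assess the significance of the difference between groups" in median stay. It adds that the median, range and quartiles will be reported. The section gives no strata, significance level, sidedness or power for this test. The logistic regression in the same section adjusts the SSI comparison only.

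Section 5.2 states: "Randomization will be stratified according to surgical site (colorectal vs hepatopancreatobiliary) and body mass index (BMI", cut at 30). It also states: "Randomization using permuted block scheme will be done via REDCap Randomization Application". Two factors with two levels each make four strata. Section 5.1 gives the size: "Up to 170 subjects will be randomized in a 1:1 ratio", "to ensure 138 evaluable subjects".

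**The concern.** Permuted blocks within site and BMI keep the arms nearly balanced on both factors. A pooled rank test takes no account of this. Its null variance is that of a simple random split of all the ranks, including the part of the spread that lies between strata. If colorectal and hepatopancreatobiliary patients stay for different lengths of time, the variance used is larger than the true variance of the statistic. The p-value is then too large on average, and a real shortening of stay is more likely to be missed.

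Section 6.1 admits operations from ileocecectomy to pancreaticoduodenectomy, so a difference in stay between sites is plausible. Length of stay is also the only secondary endpoint with a between-arm test, since the SSI subtypes are only estimated with upper confidence bounds.

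**Working it through.** **The plan's own figure.** No power is stated for length of stay. The only stated figure is about 85% for SSI, 17% v 5%, one-sided 0.10. With 69 per arm and mean rate 0.11:

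z = [0.12 × √69 − 1.2816 × √(2 × 0.11 × 0.89)] / √(0.17 × 0.83 + 0.05 × 0.95) = (0.9968 − 0.5671) / 0.4343 = 0.989, so power is 83.9%.

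That agrees with the plan to within about a point and confirms 138 evaluable (69 per arm) as the working size. Taking 170 × 0.86 = 146 instead does not change the length-of-stay results materially.

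**The two tests.**
- Wilcoxon: rank all N patients together. Without ties the null variance of the rank sum is n₁n₂(N + 1)/12, with the usual tie correction otherwise.
- Van Elteren: rank within each stratum k, then form Σ wₖ(Wₖ − Eₖ) with wₖ = 1/(Nₖ + 1) and variance Σ wₖ²Vₖ. Between-stratum spread does not enter.

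**Inputs from the documents.** 1:1 allocation, permuted blocks, four strata, up to 170 randomised, 138 evaluable.

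**Assumed inputs, because the documents give none.** Blocks of 4; 60% hepatopancreatobiliary; log-normal stay with log-SD 0.4 or 0.55; NPWT shortens stay by 15%; one-sided 0.10, borrowed from the SSI test. The unknown that matters most is the ratio of hepatopancreatobiliary to colorectal stay, so it is varied.

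**Simulated power, one-sided 0.10.** Rows for ratios 1.0, 1.5 and 2.0 include random attrition from 170 to 138. The 1.25 rows come from a run of 4,000 trials per scenario at 138 without attrition.

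| Stay ratio | Log-SD | Unstratified | Van Elteren | Difference (points) |
|---|---|---|---|---|
| 1.0 | 0.4 | 84.3% | 84.0% | −0.3 |
| 1.0 | 0.55 | 65.6% | 64.3% | −1.3 |
| 1.25 | 0.4 | 84.3% | 85.3% | +1.0 |
| 1.25 | 0.55 | 64.6% | 64.8% | +0.2 |
| 1.5 | 0.4 | 79.5% | 84.1% | +4.6 |
| 1.5 | 0.55 | 62.8% | 65.4% | +2.6 |
| 2.0 | 0.4 | 70.9% | 84.6% | +13.7 |
| 2.0 | 0.55 | 55.4% | 64.6% | +9.2 |

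With 4,000 runs, a simulated power near 84% has a standard error of √(0.84 × 0.16/4000) = 0.6 points, so differences of a point or less should not be over-read. The run without attrition gives gains of 3.2 and 2.5 points at ratio 1.5, and 12.0 and 8.4 points at ratio 2.0.

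**Size.** At ratio 2.0 the true size of the unstratified test is 0.053 to 0.074 against a nominal 0.10. The matching normal quantiles are 1.616 and 1.447. The test therefore uses a standard error about 1.616/1.282 = 1.26 to 1.447/1.282 = 1.13 times the true one.

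**Two-sided 0.05.** At ratio 2.0, power is 38.7% v 63.4% (24.7 points) at log-SD 0.4 and 25.8% v 39.0% (13.2 points) at log-SD 0.55.

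**A different set of assumptions.** Take log-SD 0.5, sites split 50/50 and a treatment effect of 0.45 SD. At site differences of 0, 0.5, 1 and 1.5 SD, van Elteren changes power by −0.6, +2.1, +7.5 and +20.4 points at two-sided 0.05, and by −0.4, +0.6, +3.5 and +7.3 points at one-sided 0.10. The one-sided gains are smaller because power is already near 90%. Van Elteren size at two-sided 0.05 stays between 4.6% and 5.1%, while the unstratified size falls from 4.9% to 1.2%.

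**The case against.** The strongest reply is that nothing here is invalid. The unstratified Wilcoxon is a legitimate test under 1:1 randomisation. Its error is in the safe direction, and the endpoint is secondary in a phase II trial with no power claim or decision rule attached. All of that stands.

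The loss is also conditional. A reader might infer that the planned test is conservative as a matter of fact. The documents do not support this, because they report no length of stay by site or BMI. Each site category also mixes short and long operations, so site may explain only part of the spread. With no site difference the loss is nil. The large losses need a ratio near 2.0, which is a shift of ln 2/0.55 = 1.26 to ln 2/0.4 = 1.73 log-SDs.

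The 15% shortening for every patient is an assumption too. The plan's rationale (Sections 1.0 and 3.0) is that infection prolongs stay. On that route, moving SSI from 17% to 5% changes stay in about 12% of patients. If an SSI is assumed to multiply stay by 1.5 to 2, power across ratios 1.0 to 2.0 is only about 17–36% unstratified and 20–37% stratified. The gap is under 2 points at ratios up to 1.25, about 2–5 at 1.5 and about 5–10 at 2.0. Stratifying would still help, but most true effects of that kind would be missed with either test. This limits the benefit of the change but does not remove the reason for it.

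**Conclusion.** The point holds in conditional form. Section 10.1 does not analyse length of stay by the groups used to randomise, and if site or BMI predicts stay the planned test is conservative and gives up power. Under the assumed inputs at one-sided 0.10, the loss is about 0 to 1 point at a stay ratio of 1.25, 2 to 5 at 1.5 and 9 to 14 at 2.0. It is larger at two-sided 0.05. The documents do not show which ratio applies.

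Two stronger readings should be resisted. A reader might infer that the length-of-stay result would be unsound, but type I error is not inflated. A reader might also infer that stratifying is free, but it can cost up to about 1 point when the strata carry no information or are very unequal. Severity is minor, and the change is optional.

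**What to change.** Replace the length-of-stay test sentence in Section 10.1 with wording such as: *Length of stay will be compared between randomised arms by the van Elteren (stratified Wilcoxon) test, stratified by surgical site and BMI group as used in the randomisation, at a significance level of [value], [one- or two-]sided; the unstratified Wilcoxon test will be reported as a sensitivity analysis.* The sponsor should fill in the level and sidedness, since one-sided 0.10 is stated for SSI only.

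The cost is one sentence and no new data, because both factors are recorded at randomisation. The downside is up to about 1 point of power if neither factor predicts stay. The change should be made before any comparison by arm. Section 10.0 reports that the study endpoint had not been analysed at the time of the amendment.

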11.0 INVESTIGATIONAL PRODUCT

The PIMS and ActiV.A.C. therapy units and associated dressings will be supplied by KCI.

Incisional NPWT will be removed prior to hospital discharge.

In the event that the clinician or study designee encounters issues with PIMS or control dressings prior to the desired time for removal, dressing replacement/reinforcement is acceptable but must be documented in the case report form (CRF). The PIMS unit may also be switched to use an ActiV.A.C unit. Any loss of negative pressure will be documented and will not determine subject evaluability. Please refer to the PIMS Instructions manual for guidance on operational questions.

A PIMS canister filled with 45 mL of wound fluid will lead to a “canister full” alarm.

11.1 INVESTIGATIONAL PRODUCT STORAGE AND ACCOUNTABILITY

The PIMS and ActiV.A.C. therapy units and associated dressings are to be stored in a secure, limited-access location with ambient room temperature away from direct sun exposure and moisture.

No investigational product will be released until the KCI receives written confirmation that the IRB has approved the clinical study.

Prior to the release of product to the site, the funding source, KCI shall complete the appropriate Investigational Product Release and Inventory Control Forms, which will accompany the shipment of the investigative product and serve as a shipping record from the funding source.

Upon receipt of product, the Principal Investigator (PI), or designee, will inventory the shipment and verify the lot numbers (PIMS) and serial numbers (ActiV.A.C units) against the information provided on the Investigational Product Release Form. The PI, or designee, will sign the form and return it to the funding source, or designee, with notations regarding any missing investigational product or other discrepancies.

The PIMS and ActiV.A.C. therapy units and associated dressings that are not dispensed for the study will be returned to KCI at the end of the study.

12.0 SAFETY REPORTING REQUIREMENTS

12.1 DEFINITIONS

The definitions in this section have been adapted from the Code of Federal Regulations (CFR) and the International Conference on Harmonization (ICH) Guidelines for Good Clinical Practices (GCPs). Please refer to the complete regulations and guidelines for additional details regarding these definitions. This study will only evaluate adverse events that are probably or possibly related to the NPWT units and dressings (e.g. blistering, redness, etc).

Adverse Event (AE) [ICH GCP]: An Adverse Event (AE) shall mean any untoward medical occurrence. For the purposes of this study, only adverse events thought to be related to the dressing will be collected and recorded.

Unanticipated adverse device effects [21 CFR 812.150]: Any serious adverse effect on health or safety, any life-threatening problem or death caused by, or associated with a device, if that effect, problem or death was not previously identified in nature, severity, or degree of incidence in the application; or any other unanticipated serious problem associated with a device that relates to the rights, safety, or welfare of subjects. An investigator shall submit to the sponsor and to the reviewing IRB a report of any unanticipated adverse device effect occurring during an investigation as soon as possible, but in no event later than 10 working days after the investigator first learns of the effect.

Deviations from the investigational plan [21 CFR 812.150]: An investigator shall notify the sponsor and the reviewing IRB of any deviation from the investigational plan to protect the life or physical well-being of a subject in an emergency. Such notice shall be given as soon as possible, but in no event later than 5 working days after the emergency occurred. Except in such an emergency, prior approval by the sponsor is required for changes in or deviations from a plan, and if these changes or deviations may affect the scientific soundness of the plan or the rights, safety or welfare of human subject, FDA and IRB approval is also required.

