3.0 STUDY RATIONALE

Patients undergoing colorectal (CRS) and hepatopancreatobiliary (HPBS) surgery are at high risk for postoperative complications such as SSI and wound dehiscence. Such complications increase the complexity of patient care during recovery from surgery, lengthen post-operative hospitalizations, add significant overall medical costs and may potentially diminish quality of life and economic livelihood. To date, there is no reported study to evaluate the efficacy of either conventional wound care with sterile dressings or the application of V.A.C.® to postoperative abdominal incisions in preventing SSI. Furthermore, there are currently no identifiable additional risks for receiving either conventional wound care or PIMS. Therefore, the proposed study will compare SSI rates for subjects receiving NPWT via PIMS or ActiV.A.C to conventional wound care with sterile dressing.

We hypothesize that incisional NPWT via PIMS or ActiV.A.C.(Kinetic Concepts USA, Inc., San Antonio, TX) compared to conventionally closed laparotomy wounds may decrease the SSI rate in these subject populations which are associated with a high rate of postoperative wound complications.

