7.0 STUDY ASSESSMENTS

7.1 STUDY CALENDAR

	Baseline ^a	Cycle Day		
		Day of Surgery	Post-op Visit 4-5 days	Post-op Visit 30 days (+/-14)
Informed Consent	X			
Demographics	X			
Medical and Surgical history	X			
Physical Exam and Vital Signs	X			
Pregnancy Test ^b	X			
Randomization ^c		X		
Incisional NPWT via PIMS or ActiV.A.C or standard wound application ^d		X		
Incision Assessment			X	X
Adverse Event Assessment		Throughout Study		
Concomitant Medication	X			

a: Screening procedures will be performed within 42 days prior to surgery.

b: Serum or urine pregnancy test in women of childbearing potential will be performed within 30 days prior to surgery

c: Randomization may occur within 5 business days of surgery.

d: Wound application will be done in the operating room by the OR team.

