7.3 EVALUATIONS DURING STUDY

7.3.1 Throughout Study

- Adverse Event evaluation specific only to the NPWT units and dressings unit (e.g. blistering, redness)

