12.2 PROCEDURES FOR REPORTING

All adverse events deemed possibly or probably related to the NPWT unit and dressings that are identified from the time of placement of the NPWT or standard of care wound application through 30 days post-surgery should be recorded on the CRFs.

Serious Adverse Events (SAEs) must ALSO be reported within 2 business days of learning of an event. The DCI Safety SAE Review Form must be completed and promptly submitted to the funding company. The forms should include at minimum the following information but should not be held until all information is available. The funding source, KCI, will be notified using the KCI USA, Inc. SAE Report Form. The Duke study team will send SAE Report Form to KCI USA, Inc. within 2 business days of knowledge of the SAE. External sites should report SAEs to the Duke study team within 24 hours. Reporting instructions for external sites can be found in the REDCap study eManual. The Duke study team will be responsible for reporting to the supporting company as well as the Duke IRB and/or FDA, where applicable. In accordance with applicable regulations, Investigators must report SAEs to their local IRB according to their institutional guidelines.

Additional information and/or corrections may be submitted as they are obtained. All SAEs must be followed through resolution or stabilization.

The initial report for each SAE should include at minimum the following information:

- protocol # and title
- patient initials, study identification number, sex, age
- date the event occurred
- description of the SAE
- description of the patient's condition
- indication whether the patient remains on study
- causality or causal relationship

SAEs should be reported by fax to the following:

KCI USA, INC
[contact]
Email: [contact]

Events will be reviewed and reported to the Duke IRB according to local IRB guidelines.

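### Local wound events other than SSI are recorded only after an open-label judgement that they are related to the NPWT unit or dressing, so by-arm counts of the safety endpoint are open to differential ascertainment

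*Combined protocol and SAP*

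**What the plan says.** Section 5.1 describes an open-label trial. It makes adverse events related to the device or dressing the safety endpoints, and counts abnormal skin findings such as blisters or rash among them.

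Three places restrict what reaches the safety data:

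- Section 12.1 opens with "This study will only evaluate adverse events that are probably or possibly related to the NPWT units and dressings". Its definition of an adverse event adds that "only adverse events thought to be related to the dressing will be collected and recorded".
- Section 7.3.1 confines evaluation during the study to the NPWT units and their dressings, with blistering and redness as examples.
- Section 12.2 sets the rule for the case report form: "All adverse events deemed possibly or probably related to the NPWT unit and dressings that are identified from the time of placement". Placement here means either the NPWT or the standard wound application, so control subjects are in scope.

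No section names who judges relatedness, gives criteria for it, or describes an assessor blinded to arm.

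On the window, Section 5.1 says "These endpoints will be assessed from the day of surgery through the 30-day follow-up visit", and Sections 7.1 and 7.3.4 allow that visit 14 days either side of day 30. Section 12.2 says events "through 30 days post-surgery should be recorded on the CRFs".

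Section 3.0 calls these patients "at high risk for postoperative complications such as SSI and wound dehiscence". Section 10.1 plans no between-arm safety test.

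**The concern.** Relatedness is normally a field recorded about an event. Here it decides whether the event is recorded. An event judged unrelated leaves no adverse event record, so nobody can later re-adjudicate it or count it by arm.

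The judgement is made with the arm known, or at least nothing in the plan prevents that. It is also worded mainly around equipment that only the experimental arm wears. A blister under the NPWT dressing is easily ascribed to it. The same finding beside a gauze dressing may be put down to the operation, the staples or the skin, and then not recorded. The opposite error is possible too: wound breakdown under NPWT may be blamed on surgery and disappear.

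At stake is the reading of the safety endpoint. Its by-arm counts could show an excess under NPWT that is not real, or fail to show one that is. The primary SSI comparison is not at stake on this point.

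**Working it through.** **1. Which events pass through the filter.** The plan has two routes by which a wound event can be captured.

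| Event | Route | Attribution to dressing needed? |
|---|---|---|
| SSI of any class (Sections 5.1, 8.0) | Determined at day 4-5 and at the clinic visit, both arms | No |
| Deep dehiscence with fever, pain or tenderness, not culture-negative (Section 8.0) | Can qualify as deep incisional SSI | No |
| Dehiscence without infection | Adverse event | Yes |
| Blister, rash, or redness not diagnosed as SSI | Adverse event | Yes |

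Both post-operative visits include an incision assessment in all subjects (Sections 7.1, 7.3.3, 7.3.4), but no list of wound findings is given. The principal investigator's confirmation is directed only to findings that suggest infection. Non-infectious local events therefore have no stated route other than the filtered one.

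**2. How far differential recording could distort the counts.** The plan gives no adverse event rate and no figure to reproduce. All rates below are assumptions.

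- Let p be the true event rate, the same in both arms, and let cN and cC be the proportions of events judged related and recorded under NPWT and control.
- Recorded rates are p × cN and p × cC. The apparent risk ratio is (p × cN)/(p × cC) = cN/cC, which does not depend on p.
- Arm size for expected counts: 138 evaluable / 2 = 69 (Section 5.1).

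| cN | cC | Apparent risk ratio | Expected counts, p = 5% | p = 10% | p = 20% |
|---|---|---|---|---|---|
| 0.9 | 0.9 | 0.9/0.9 = 1.00 | 3.1 vs 3.1 | 6.2 vs 6.2 | 12.4 vs 12.4 |
| 0.9 | 0.7 | 0.9/0.7 = 1.29 | 3.1 vs 2.4 | 6.2 vs 4.8 | 12.4 vs 9.7 |
| 0.9 | 0.5 | 0.9/0.5 = 1.80 | 3.1 vs 1.7 | 6.2 vs 3.5 | 12.4 vs 6.9 |
| 0.9 | 0.3 | 0.9/0.3 = 3.00 | 3.1 vs 1.0 | 6.2 vs 2.1 | 12.4 vs 4.1 |

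Example: at p = 10% and cN = 0.9, 69 × 0.10 × 0.9 = 6.2. A more extreme assumption of 80% against 20% at p = 10% gives 8% against 2%. If every event is blamed on surgery, the record shows 0% against 0% whatever the true rates.

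**3. The window.** The 30-day visit can fall from day 30 − 14 = 16 to day 30 + 14 = 44. The Section 5.1 window can therefore close up to 14 days before or 14 days after the fixed day 30 of Section 12.2. Both apply to all subjects. The mismatch leaves unclear which events count, but it acts alike in the two arms.

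**The case against.** The strongest reply is that Section 12 does not contradict Section 5.1. The safety endpoint is itself defined as related events, so the filter applies it. Restricting adverse event collection for 510(k)-cleared devices is a deliberate choice, the threshold of possible relatedness is low, and Section 10.1 plans no safety test that could be biased. This stands in part. There is no contradiction, and limiting systemic events is defensible. But a by-arm count of a named safety endpoint will be read comparatively whether or not it is tested, and a low threshold narrows a difference in recording without ruling it out.

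A second reply is that other data exist. Side effects and symptoms are reviewed at both visits, postoperative variables are collected and tabulated (Sections 10.0, 10.1), and dressing problems in either arm that lead to replacement or reinforcement must be documented (Section 11.0). The case report form is not among the documents, so some local findings may be captured there. The plan does not say that they are.

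A reader might infer three stronger things that the documents do not support:

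- That local wound harms cannot be compared between arms at all. SSI, including some symptomatic deep dehiscence, is captured in both arms without attribution.
- That dehiscence is a study target that the plan then fails to collect. Section 3.0 names it as a risk of this population; the hypothesis and objectives concern SSI, its classes and length of stay.
- That the two windows bias the comparison. Neither is specific to an arm.

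**Conclusion.** The point holds for local wound events other than SSI. The plan makes a relatedness judgement, unprotected by blinding and worded mainly around the NPWT unit, the condition for recording them. By-arm counts of the Section 5.1 safety endpoint are therefore open to differential ascertainment, with no adverse event record from which to correct it. That whoever assesses relatedness knows the arm is inferred from the open-label design and the absence of any blinded assessor; the documents do not state it.

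The size is unknown. Under the assumed recording proportions, the apparent risk ratio ranges from 1.0 (equal recording) to 3.00 (90% against 30%) with no true difference. The expected counts behind these ratios are small, and true harm could equally be hidden. The primary analysis is untouched by this filter.

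The window mismatch is real but is a separate point of consistency.

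**What to change.** At the two existing incision assessments, record a short present/absent list of local wound findings (for example blister, rash, redness, dehiscence) in both arms regardless of cause. Keep relatedness as a separate field, and add to Section 10.1 a tabulation of the list by arm. Amend Sections 7.3.1, 12.1 and 12.2 so that the relatedness restriction no longer governs these items. Systemic events can stay limited to related ones.

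Timing limits what this achieves. Section 10.0 reports 143 of up to 170 patients already enrolled, leaving 27 (27/170 = 16%) for fully prospective use, plus any enrolled patients still awaiting an assessment. For subjects already assessed, abstract the same items from the chart where documented, and flag the data source. Sections 7.3.3 and 7.3.4 already let these visits be done by review of clinical data.

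The cost is modest extra data entry and a mixture of prospective and retrospective ascertainment, which the report should show. No new visit or procedure is needed. The list would still be completed open-label, so it reduces the bias and does not remove it.

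Separately, reconcile the end of the adverse event window between Section 5.1 and Section 12.2, and state one rule in both.
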